## 6.2 Dose Modifications Due to Non-Hematologic Toxicity

Dose modifications due to non-hematologic toxicities are shown in [Table 6](#).

**Table 6 Dose Modifications due to Grade 3 or 4 Non-Hematologic Toxicities**

Toxicity Grade	AC176 Dose a
Grade 3 (except nausea, vomiting, alopecia, diarrhea, rash, and fatigue)	Hold a until recovery to $\leq$ Grade 1 or baseline
Toxicity resolves in $\leq$ 7 days	Resume at original dose.
Toxicity resolves $>$ 7 day and $<$ 2 weeks	Reduce by 1 dose level.
Toxicity does not resolve to $\leq$ Grade 1 or baseline within 2 weeks	Discontinue treatment. If in the patient's best interest, dose may be resumed at a lower dose only after discussion and agreement with Medical Monitor.
Recurrence of the above same toxicity	Hold a until recovery to $\leq$ Grade 1 or baseline
Toxicity resolves $\leq$ 7 days	Resume at original dose or reduce by 1 dose level at the Investigator's discretion b
Toxicity resolves $>$ 7 days	Discontinue treatment. If in the patient's best interest, dose may be resumed at 1 reduced dose level only after discussion and agreement with Medical Monitor
Grade 4 (except asymptomatic electrolyte abnormalities that respond to treatment and resolve to $\leq$ Grade 2 within 72 hours, nausea, vomiting, alopecia, diarrhea, rash, and fatigue)	Discontinue treatment.
Grade 4 asymptomatic electrolyte abnormalities that respond to treatment and resolve to $\leq$ Grade 2 within 72 hours	Hold a Once resolved as mentioned, treatment may continue at 1 reduced dose level at the Investigator's discretion and upon discussion with Medical Monitor
Grade 3 or 4 nausea, vomiting diarrhea, rash, or fatigue	Hold and institute maximum supportive treatment until recovery to $\leq$ Grade 1, baseline or tolerable Grade 2
Toxicity resolves $\leq$ 7 days	Resume at original dose.
Toxicity resolves $>$ 7 day and $<$ 2 weeks	Reduce by one dose level b

Toxicity Grade	AC176 Dose a
Toxicity does not resolve to $\leq$ Grade 1 or baseline, or tolerable Grade 2 by 2 weeks	Discontinue treatment. If in the patient's best interest, dose may be resumed at a lower dose only after discussion and agreement with Medical Monitor
Recurrence of the above same toxicity	Hold and institute maximum supportive treatment until recovery to $\leq$ Grade 1, baseline or tolerable Grade 2
Toxicity resolves $\leq$ 7 days	Resume at original dose or reduce by one dose level at the Investigator's discretion b
Toxicity resolves $>$ 7 days	Discontinue treatment. If in the patient's best interest, dose may be resumed at a lower dose only after discussion and agreement with Medical Monitor

a AC176 should be held until toxicity resolves to  $\leq$  Grade 1 or baseline. Any patients who develop irreversible Grade 3/4 non-hematologic toxicity that does not resolve to  $\leq$  Grade 1 or baseline within 2 weeks after maximum supportive treatment should be removed from the study unless the treating physician and the Medical Monitor agree that continued treatment at lower doses is in the best interest of the patient.

b No more than 2 dose reductions of AC176 are allowed unless the treating physician and the Medical Monitor agree that continued treatment at lower doses is in the best interest of the patient.

### 6.2.1 Specific Recommendations for Liver Function Test Abnormalities

For patients with Grade 3 liver enzyme elevations (AST/ALT), AC176 should be held until the values recover to  $\leq$  Grade 1 or baseline. Patients with an elevation of AST/ALT  $\geq 3 \times$  ULN in conjunction with a bilirubin  $\geq 2 \times$  ULN may remain in the study if a correctable, non-drug related cause of the liver test evaluations can be documented; otherwise, the patient must be discontinued from the study.

## 7. STUDY ASSESSMENTS AND EVALUATIONS

### 7.1 Overview

All patients should visit the study center on the days specified within this protocol. The complete Schedule of Assessments for this study is presented at the beginning of this protocol (see [Table 2](#) or the appropriate SOA table in [Appendix H](#)). The key procedures required in this study include:

- Reporting of all AEs occurring after the main ICF has been signed
- Laboratory assessments (blood and urine based)
- Immature platelet fraction testing (blood based), at sites with the capability, and if clinically indicated
- PK samples throughout the study
- Baseline and on-treatment blood biomarker assessments

*CONFIDENTIAL*

Study Drug: AC176

Sponsor/Development Innovations Study Number: AC176-001/GU 207

Final Protocol: 10 July 2023 Version 4.0

- Tumor biopsy biomarker assessments
- Tumor assessments (based on CT/MRI and bone scans according to Response Evaluation Criteria in Solid Tumors (RECIST) Version 1.1 and PCWG3 (see [Appendix B](#)).
- PSA assessments

Treatment cycle is presented in the SOA table or assigned at patient enrollment. Multiple procedures may be scheduled at the same time point relative to AC176 dosing. Priority should be given to PK collection at the time specified. Vital signs and ECG assessments should be performed prior to specimen collections.

## 7.2 Pre-Screening AR Mutation Status for Backfill Patients and Expansion Cohorts

Prostate cancers with AR mutations are more dependent on the AR pathway for their growth. Degradation of AR makes these cancers more susceptible to cell death. Thus, AR-mutated cancers may respond to AR degradation at lower doses than their wildtype counterparts.

Pre-screening, as described in [Table 1](#), for AR mutation status is required in the Backfill and Expansion cohorts. If patients provide historic ctDNA testing results of a positive AR point mutation, then pre-screening ctDNA testing for AR mutation status by ctDNA testing is not needed. All patients will retrospectively undergo central laboratory testing for AR mutation confirmation at Cycle 1 Day 1 per the SOA.

Patients who have not had AR point mutation testing must agree to sign a pre-screening ICF to collect a blood sample for ctDNA. Confirmation of the AR point mutation does not guarantee eligibility for a backfill cohort or the expansion cohort.

Depending on the AR point mutation status, patients may proceed with further screening procedures for Backfill or Expansion cohorts, as appropriate, after signing a separate ICF for the study.

## 7.3 Screening

At enrollment, each potential research subject will provide written informed consent  $\leq 28$  days prior to initiation of treatment and prior to starting any study-specific procedures. Upon signature of the ICF, patients will be assigned a unique subject number as enrollment (screening) occurs.

The screening assessments described in [Table 1](#) will be collected, reviewed, and determined to be acceptable by the site Principal Investigator or designee after obtaining informed consent prior to the initiation of treatment. Patients who do not meet all inclusion criteria, or who meet an exclusion criterion, may be rescreened once. Rescreening is at the discretion of the Investigator but requires Sponsor approval and agreement.

The following information will be collected and procedures will be performed  $\leq 28$  days prior to initiation of treatment:

- Written informed consent prior to any other study-related procedures
- Medical history, concomitant therapy, and demographics
- Adverse events
- ECHO

*CONFIDENTIAL*

Study Drug: AC176

Sponsor/Development Innovations Study Number: AC176-001/GU 207

Final Protocol: 10 July 2023 Version 4.0

- Serology infection test (Hepatitis B Virus Surface Antigen (HBsAg), Anti-HBc, Hepatitis B DNA, Hepatitis C Virus antibody, Hepatitis C RNA, Human Immunodeficiency Virus 1 [HIV-1], Human Immunodeficiency Virus 2 [HIV-2])
- Pre-treatment biopsy (optional)
- Testosterone blood level
- PSA level
- CT scan/MRI of chest, abdomen, and pelvis
- Bone scan

The following screening parameters should be recorded  $\leq 14$  days prior to initiation of treatment:

- Physical examination (including height and weight)
- ECOG performance status
- 12-lead ECG triplicate
- Vital signs (blood pressure, body temperature, pulse rate, and respiration rate)
- Hematology
- Biochemistry (sodium, potassium, phosphate, chloride, creatinine, calcium, venous bicarbonate  $\text{HCO}_3$ , albumin, total protein, AST, ALT, ALP, total bilirubin, lactate dehydrogenase, serum glucose, creatinine kinase [CK: if CK is elevated, then CK-MB, troponin I, and myoglobin should be reactively tested, with further follow-up as clinically warranted], serum urea nitrogen, and serum uric acid)
- Thyroid stimulating hormone [TSH] and free T4
- Urinalysis

If these assessments are performed within 72 hours of initiation of treatment, they do not need to be repeated on Cycle 1 Day 1, with the exception of ECOG performance status, an abbreviated physical examination (head, eyes, ears, nose and throat, as appropriate), vital signs, and triplicate ECGs.

Relevant concomitant diagnoses and/or therapies present at study entry and/or during screening that are relevant to the patient's safety during the study (as judged by the Investigator) will be recorded in the eCRF (see Section 5.3 for details on concomitant medications).

#### 7.4 Assessments During Study Treatment

Patients will remain on treatment as long as, in the opinion of the Investigator, they are deriving benefit and the criteria listed in Section 7.6 are not met. Please refer to the applicable SOA table for detailed outlines of each visit during the treatment period for each part of the study.

*CONFIDENTIAL*

Study Drug: AC176

Sponsor/Development Innovations Study Number: AC176-001/GU 207

Final Protocol: 10 July 2023 Version 4.0

#### **7.4.1 Response Assessments**

Patients will be evaluated for response to treatment every 2 cycles  $\pm 5$  days up to 24 weeks (if 28 day cycle) or up to 18 weeks (if 21 day cycles), then every 12 (or 9, respectively) weeks  $\pm 5$  days, and, if clinically indicated, imaging of any other known or suspected sites of disease (e.g., brain).

The following assessments will be performed in addition to determination of elevated PSA levels (which will be taken on prior to dosing on Cycle 1 Day 1 as PSA baseline and on Day 1 of each subsequent cycle):

- CT/MRI scans of chest
- CT/MRI scan of the abdomen and pelvis
- Bone scan - technetium only

Lymph nodes and bone lesions should be evaluated using PCWG3 criteria ([Appendix B](#)) not RECIST v1.1. Patients with progressive disease or unacceptable toxicity should be discontinued from the study; patients with stable disease (SD) or response to therapy may continue treatment.

#### **7.4.2 PSA Progression**

PSA progression is defined as  $\ge 25\%$  increase and  $\ge 2$  ng/mL increase above the nadir or baseline value for patients who had a PSA decrease on treatment, which is confirmed by a second value 3 or more weeks later.

For patients without a decrease on treatment, PSA progression is defined as a  $\ge 25\%$  increase and an absolute increase of  $\ge 2$  ng/mL after 12 weeks.

PSA progressions must be confirmed at the next study visit 4 weeks later. PSA will be collected at screening and on Day 1 of each treatment cycle.

#### **7.4.3 PSA Response**

PSA response is defined as the proportion of patients achieving a  $\ge 50\%$  decline from baseline to the lowest post-baseline PSA results, confirmed by a second consecutive PSA assessment at least 3 weeks later. Ignore early rises (before 12 weeks) in determining PSA response.

- A patient will be regarded as having a single PSA visit response if their PSA level at any post-dose visit is reduced by 50% or more compared with baseline
- A patient will be regarded as having a confirmed PSA response if they have a reduction in PSA level of 50% or more compared with baseline that is confirmed at the next assessment at least 3 weeks later (i.e., decrease relative to baseline of at least 50% documented on 2 consecutive occasions at least 3 weeks apart).

### **7.5 Follow-Up Periods and Study Completion**

#### **7.5.1 End-of-Treatment Visit**

The EOT visit will be performed as soon as possible (preferably within 7 days but no later than 14 days) after permanent discontinuation of the study treatment for any reason, or when the Investigator decided with the patient to permanently discontinue the study treatment, or when the Investigator became aware that the study treatment had been discontinued.

*CONFIDENTIAL*

Study Drug: AC176

Sponsor/Development Innovations Study Number: AC176-001/GU 207

Final Protocol: 10 July 2023 Version 4.0

The assessments of the EOT visit will then be performed at the next planned visit. If the patient finishes treatment without having progressive disease (PD), tumor assessment/imaging must be performed at the time of treatment discontinuation unless it has been done within the past 4 weeks.

### **7.5.2 Thirty-Day Safety Follow-up**

All patients will be followed during the off-treatment period until all treatment-related toxicity resolves, or for at least 30 days post-study drug discontinuation, or until the start of another anti-cancer treatment. Any concomitant medications received up to 30 days after the last dose of study medication should be recorded.

### **7.5.3 Extended Follow-Up Period**

If treatment was discontinued for reasons other than disease progression, additional follow-up visits after the 30-day safety follow-up visit will be performed for tumor assessment by imaging as on treatment until PD or another withdrawal criterion is met:

- Start of a new anti-cancer therapy
- Lost to follow-up
- Death
- Patient withdrawal
- End of the whole study.

Additional PSA assessments after the 30-day safety follow-up visit will be performed as on treatment until PD or another withdrawal criterion is met.

These visits may also be performed by telephone interview or via written correspondence in case the patient is unable to visit the Investigator.

## **7.6 Early Patient Termination/Patient Withdrawal**

Patients who discontinue treatment early due to disease progression, unacceptable toxicity, intolerance, or withdrawal of consent will be asked to have all EOT safety evaluations performed as described in the protocol (see the applicable SOA table). If a patient withdraws from treatment during Cycle 1 due to any reason other than a DLT and does not meet the minimum requirements for inclusion in the MTD-determining population described in Section 5.1.4, that patient will be replaced.

## **7.7 Pharmacokinetic Assessments**

Serial blood (plasma) samples will be collected to assess the pharmacokinetics of AC176. Any residual plasma from the collected pharmacokinetic samples may be used for metabolite analysis, when an assay becomes available.

Meal consumption prior to full 24-hour PK collections will be collected. The last meal consumed prior to dosing on the day of full PK collections during Cycle 1 should be recorded.

If the sample cannot be collected at the visit as scheduled, it should be collected at the next visit whenever possible. Additional unscheduled PK samples may be drawn during the study if it is deemed clinically indicated for the patient and/or based on newly emerged data from clinical

*CONFIDENTIAL*

Study Drug: AC176

Sponsor/Development Innovations Study Number: AC176-001/GU 207

Final Protocol: 10 July 2023 Version 4.0

studies of AC176. Similarly, if any PK timepoint is later deemed unnecessary per acquired clinical PK data, such timepoint may be removed from PK schedule by the Sponsor.

With Sponsor approval the required 10 hour and 12 hour PK sample collections may be omitted if not feasible.

The schedule for PK assessments is found in [Appendix G](#).

## **7.8 Biomarker Assessments**

### **7.8.1 Optional Fresh Biopsies**

Fresh tumor biopsies at baseline and on-treatment are optional. All fresh biopsies will be processed according to the laboratory manual.

Evaluable baseline and on-treatment biopsy samples will be used to evaluate the amount of AR degradation during treatment. If possible, sites should collect pre- and on-treatment biopsies from the same tumor lesion. Accessible lesions are defined as tumor lesions that can be biopsied and that are amenable to repeat biopsy unless clinically contraindicated or the patient has withdrawn consent.

If a patient agrees to baseline biopsy and on-treatment biopsies, the equivalent of four 18-gauge core needle biopsies will be freshly taken between screening and the day before the first study drug treatment. Another equivalent of four 18-gauge core needle biopsies will be collected on Cycle 2 Day 1 (+ 5 days).

Biopsies should be obtained through non-significant risk procedures. Sampling should be undertaken by experienced physicians in appropriate settings.

Instructions regarding sample collection, handling/processing and shipping are provided in the Laboratory Manual.

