Evaluate the effect of AC176 on progression-free survival (PFS)	PFS based on PCWG3-modified RECIST v1.1 and/or PCWG3 PSA criteria. PFS is defined as the time from first study drug administration until objective disease progression (based on bone or CT/MRI scans), or PSA, or death, whichever occurs first.
Exploratory Objectives:	Endpoint/Variable:
Evaluate the relationship between AR degradation on tumor tissue and administration of AC176	Change of AR expression in tumors from baseline to post-treatment, if tumor tissue is available from paired biopsies
Evaluate the relationship between AR degradation in circulating tumor cells (CTCs) and administration of AC176, if available	Change of AR expression in CTCs from baseline to post-treatment
Evaluate the relationship of CTC numbers (baseline and post-treatment) and anti-tumor activity of AC176, if available	Baseline CTC numbers or changes of CTC numbers post-treatment. Correlation to anti-tumor activity (PSA response rate, ORR, rPFS, PFS, DoR and TTP)

Objectives:	Endpoint/Variable:
Evaluate the relationship of nuclear ARv7 expression (baseline and post-treatment) and anti-tumor activity of AC176	Baseline ARv7 nuclear expression and changes of ARv7 nuclear expression post-treatment in CTCs. Correlation to anti-tumor activity (PSA response rate, ORR, rPFS, PFS, DoR and TTP)
Evaluate the relationship between baseline AR genomic profiles and anti-tumor activity of AC176	AR genomic profiles by circulating tumor DNA (ctDNA). Correlation to anti-tumor activity (PSA response rate, ORR, rPFS, PFS, DoR and TTP)

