- h Expansion Cohort PKs samples should be collected pre-dose on Cycle 2 Day 15, Cycle 4 Day 15 and Cycle 6 Day 15. Triplicate ECGs will be obtained before the pre-dose PK collection on Day 15 of Cycle 2. No full day PK are required. Additional unscheduled PK samples may be drawn during the study if it is deemed clinically indicated for the patient and/or based on newly emerged data from clinical studies of AC176. The visit days and sampling time points are outlined in [Appendix G](#).
- i Fresh tumor biopsies on treatment are optional. If patient agrees to anon-treatment biopsies, the biopsy will be collected on Cycle 2 Day 1 (+ 5 days) (see Section [7.8.1](#)).
- j All patients will retrospectively undergo central laboratory testing for AR mutation confirmation at predose C1D1. Blood samples for ctDNA will be collected prior to dosing at predose Cycle 1 Day 1, and on Cycle 2 Day 1, Cycle 5 Day 1, and Cycle 8 Day 1, and at EOT as outlined in Section [7.8.2](#).
- k Blood samples for ARv7 testing will be collected prior to dosing at Cycle 1 Day 1 and at EOT as outlined in Section [7.8.2](#).
- l Dosing and schedule of AC176 will be determined by the Safety Review Committee and communicated separately as each new cohort opens for recruitment. Patients will be instructed to take one dose of AC176 at the same time every day immediately after a meal. The patients will be asked to take AC176 in the morning immediately after a meal, and other concomitant medications in the evening; or at least 4 hours apart from taking AC176, if possible.  
Study drug compliance will be assessed at each patient visit by review of the dosing diary.

CONFIDENTIAL

Study Drug: AC176

Sponsor/Development Innovations Study Number: AC176-001/GU 207

Final Protocol: 10 July 2023 Version 4.0

- m Prostate-specific antigen (PSA) blood samples will be taken prior to dosing Cycle 1 Day 1 (unless collected within the previous 72 hours), and at Day 1 of every cycle, and at the EOT visit if not taken in the previous 4 weeks, and at progression. Additional PSA assessments after the 30-day safety follow-up visit will be performed as on treatment until PD or another withdrawal criterion is met..

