Table 14: 3 weeks on and 1 week off: Pharmacokinetic(PK) sampling will be collected on Cycle 1 Day 1 and 8 pre-dose and post-dose at: 1 and 2 hours ( $\pm$ 5 minutes), 3 and 4 hours ( $\pm$ 10 minutes), 6 ( $\pm$ 20 minutes), 8, 10 and 12 hours ( $\pm$ 1 hour), and 24-hours post dose ( $\pm$ 1 hour). In addition to the pre-dose ECGs collected on Cycle 1 Day 1 and 8, triplicate ECGs will also be obtained on Cycle 1 Day 1 and 8 just before the 4-hour and 8-hour post-dose PK blood samples are collected. On Cycle 2 Day 22, Cycle 4 Day 22, and Cycle 6 Day 22, a pre-dose PK sample will be collected from all patients. Triplicate ECGs will be obtained before the pre-dose PK collection on Day 22 of Cycle 2, Cycle 4 and Cycle 6.
- h Expansion Cohort (Part B) PKs sample collections are different from Part A cohort collections. For 3 weeks on and 1 week off dosing schedule: the Expansion Cohort PKs are collected on Day 22 of Cycle 2, Cycle 4, Cycle 6. Triplicate ECGs will be obtained before the pre-dose PK collection on Day 22 of Cycle 2. For 2 weeks on and 2 week off dosing schedule: the Expansion Cohort PKs are collected on Day 15 of Cycle 2, 4, and 6. Triplicate ECGs will be obtained before the pre-dose PK collection on Day 15 of

CONFIDENTIAL

Study Drug: AC176

Sponsor/Development Innovations Study Number: AC176-001/GU 207

Final Protocol: 10 July 2023 Version 4.0

Cycle 2. No full day PKs are required for the Expansion cohort. Additional unscheduled PK samples may be drawn during the study if it is deemed clinically indicated for the patient and/or based on newly emerged data from clinical studies of AC176. The visit days and sampling time points are outlined in [Appendix G](#).

- i Fresh tumor biopsies at on treatment are optional. If patient agrees to an on-treatment biopsy, it will be collected on Cycle 2 Day 1 (+ 5 days) (see Section [7.8.1](#)).
- j All patients will retrospectively undergo central laboratory testing for AR mutations confirmation at C1D1. Blood samples for ctDNA will be collected prior to dosing at predose Cycle 1 Day 1, and on Cycle 2 Day 1, Cycle 5 Day 1, and Cycle 8 Day 1, and at EOT as outlined in Section [7.8.2](#).
- k Blood samples for ARv7 testing will be collected prior to dosing at Cycle 1 Day 1 and at EOT as outlined in Section [7.8.2](#).
- l Dosing and schedule of AC176 will be determined by the Safety Review Committee and communicated separately as each new cohort opens for recruitment.  

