Patients dosing schedule may include:
  - 1) 2 weeks on 2 weeks off, e.g., C1D1 to C1D14 receive AC176. Dose is interrupted C1D15 to C1D28. AC176 dose to continue C2D1 to C2D14. Dose is interrupted C2D15 to C2D28, etc.
  - 2) 3 weeks on 1 week off, e.g., C1D1 to C1D21 receive AC176. Dose is interrupted C1D22 to C1D28. AC176 dose to continue C2D1 to C2D21. Dose is interrupted C2D22 to C2D28, etc.

Patients will be instructed to take one dose of AC176 at the same time every day immediately after a meal. The patients will be asked to take AC176 in the morning immediately after a meal, and other concomitant medications in the evening; or at least 4 hours apart from taking AC176, if possible.

Study drug compliance will be assessed at each patient visit by review of the dosing diary.

- m Prostate-specific antigen (PSA) blood samples will be taken prior to dosing Cycle 1 Day 1 (unless collected within the previous 72 hours), and at Day 1 of every cycle, and at the EOT visit if not taken in the previous 4 weeks, and at progression. Additional PSA assessments after the 30-day safety follow-up visit will be performed as on treatment until PD or another withdrawal criterion is met.
- n CT/MRI scans of the chest, abdomen and pelvis should be taken  $\leq$  4 weeks prior to initiation of treatment. CT/MRI scans of the chest, abdomen, and pelvis should be taken every 2 cycles (8 weeks)  $\pm$  5 days up to 24 weeks, then every 12 weeks  $\pm$  5 days, and at the End of Study visit (if scans were not taken in the previous 8 weeks) and, if clinically indicated, imaging of any other known or suspected sites of disease (e.g., brain). Lymph nodes should be evaluated using PCWG3 criteria and not RECIST v1.1.
- o Bone scans - technetium only -  $\leq$  4 weeks prior to initiation of treatment, every 2 cycles (8 weeks)  $\pm$  5 days up to 6 cycles (24 weeks), then every 3 cycles (12 weeks)  $\pm$  5 days, and at the End of Study visit if scans were not taken in the previous 8 weeks. Bone lesions should be evaluated using PCWG3 criteria and not RECIST v1.1.
- p An EOT visit should be performed for all patients who permanently discontinue study treatment. If the decision to permanently discontinue treatment is made at a scheduled visit, the EOT visit should be performed instead of the scheduled visit (preferably within 7 days and no later than 14 days after the last treatment).

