i Fresh tumor biopsies on treatment are optional. If patient agrees to an on-treatment biopsies, the biopsy will be taken on Cycle 2 Day 1 (+ 5 days) (see Section [7.8.1](#)).

j All patients will retrospectively undergo central laboratory testing for AR mutation confirmation at C1D1. Blood samples for ctDNA will be collected prior to dosing at predose Cycle 1 Day 1, and on Cycle 2 Day 1, Cycle 5 Day 1, and Cycle 8 Day 1, and at EOT as outlined in Section [7.8.2](#).

k Blood samples for ARv7 testing will be collected prior to dosing at Cycle 1 Day 1 and at EOT as outlined in Section [7.8.2](#).

l Patients dosing schedule may include:

1. 7 days on and 7 days off, e.g., C1D1 to C1D7 receive AC176. Dose interrupted C1D8 to C1D14. AC176 dose to continue Cycle 1 on C1D15 to C1D21 and interrupted C1D22 to C1D28. From Cycle 2, the patients will be dosed for 7 days and interrupted 7 days.
2. Patients will be dosed 5 days on and 2 days off, e.g., C1D1 to C1D5 receive AC176. Dose interrupted C1D6 to C1D7. AC176 dosed to continue Cycle 1 on C1D8 to C1D12 and interrupted C1D13 to C1D14. C1D15 to C1D19 receive AC176. Dose interrupted C1D20 to C1D21. AC176 dosed to continue Cycle 1 on C1D22 to C1D26 and interrupted C1D27 to C1D28.
3. Patients will be dosed one week 4 days on and one week 3 days off, e.g., C1D1 to C1D4 receive AC176. Dose interrupted C1D5 to C1D7. AC176 dosed to continue Cycle 1 on C1D8 to C1D11 and interrupted C1D12 to C1D14. C1D15 to C1D18 receive AC176. Dose interrupted C1D19 to C1D21. AC176 dosed to continue Cycle 1 on C1D22 to C1D25 and interrupted C1D26 to C1D28.

Patients will be instructed to take one dose of AC176 at the same time every day immediately after a meal. The patients will be asked to take AC176 in the morning immediately after a meal, and other concomitant medications in the evening; or at least 4 hours apart from taking AC176, if possible. Study drug compliance will be assessed at each patient visit by review of the dosing diary.

m Prostate-specific antigen (PSA) blood samples will be taken  $\leq$ 4 weeks prior to initiation of treatment, prior to dosing Cycle 1 Day 1 (unless collected within the previous 72 hours), and at Day 1 of every cycle, and at the EOT visit if not taken in the previous 4 weeks, and at progression. Additional PSA assessments after the 30-day safety follow-up visit will be performed as on treatment until PD or another withdrawal criterion is met.

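### On the intermittent schedules the on-treatment biopsy stays at C2D1 (+5 days), so it can fall anywhere from the end of the off-drug block to several doses into re-dosing and does not reliably measure AR degradation during treatment

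*Protocol*

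**What the plan says.** Section 7.8.1 gives the purpose of the biopsy pair: "Evaluable baseline and on-treatment biopsy samples will be used to evaluate the amount of AR degradation during treatment". The endpoint it serves, in the exploratory part of Table 3, is "Change of AR expression in tumors from baseline to post-treatment, if tumor tissue is available from paired biopsies". Both biopsies are optional.

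The day of the second biopsy is the same everywhere. Section 7.8.1 says "Another equivalent of four 18-gauge core needle biopsies will be collected on Cycle 2 Day 1 (+ 5 days". Footnote i in Appendix H repeats that day for the intermittent schedules:
- SOA 3 (2 weeks on/1 off, 21-day cycle): "the biopsy will be collected on Cycle 2 Day 1 (+ 5 days".
- SOA 4 (3 weeks on/1 off, or 2 weeks on/2 off): "If patient agrees to an on-treatment biopsy, it will be collected on Cycle 2 Day 1 (+ 5 days".
- SOA 5 (7/7, 5/2 and 4/3 days): "the biopsy will be taken on Cycle 2 Day 1 (+ 5 days".

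Each of these schedules ends Cycle 1 without drug. For 2 weeks on/2 off, SOA 4 footnote l says "Dose is interrupted C1D15 to C1D28", with dosing resuming on C2D1. The protocol does not say whether a C2D1 biopsy comes before or after that day's dose.

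The Cycle 2 pre-dose PK sample, by contrast, was re-timed for each schedule: C2D15 for 2/2 and 2/1, C2D22 for 3/1, C2D8 for 7/7, C2D6 for 5/2 and C2D5 for 4/3 (Appendix G, Tables 9 to 14, and footnote g of SOA 3 to 5).

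**The concern.** Under continuous dosing, C2D1 follows 28 dosed days, so a biopsy there is a true on-treatment sample. On an intermittent schedule the same calendar day is the end of an off-drug block. The +5-day window then runs into the resumed on-block. Two patients on one dose and schedule can be sampled in very different states of exposure, and nothing in the plan separates them.

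At stake is whether the paired biopsies can answer the question they are taken for. They are the only scheduled measurement of AR protein during treatment: the blood sample for circulating tumor cells is drawn only at C1D1 and at end of treatment (Section 7.8.2). Section 5.1.1 also gives biopsy data as one reason for enrolling additional patients at lower doses. That the PK day was adapted and the biopsy day was not, with no reason given, suggests that the biopsy day was carried over from continuous dosing.

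**Working it through.** There is no figure in the plan to reproduce; the check is a day count from its calendars.

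**1. Gap from the last Cycle 1 dose to C2D1.** Inputs are the cycle length and last dosing day (Table 16 for 2/1; SOA 4 footnote l for 2/2 and 3/1; SOA 5 footnote l for 7/7, 5/2 and 4/3).

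Gap = cycle length + 1 − last dosing day. Drug-free days = gap − 1.

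**2. Resumed doses at the end of the window (C2D6).** Count the dosing days before C2D6. For 5/2 and 4/3 this assumes that the Cycle 1 pattern repeats in Cycle 2.

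| Schedule | Cycle length | Last dose | Gap (days) | Drug-free days | Resumed doses before C2D6 |
|---|---|---|---|---|---|
| 2 weeks on/2 off | 28 | D14 | 29 − 14 = 15 | 14 | 5 |
| 3 weeks on/1 off | 28 | D21 | 29 − 21 = 8 | 7 | 5 |
| 2 weeks on/1 off | 21 | D14 | 22 − 14 = 8 | 7 | 5 |
| 7 days on/7 off | 28 | D21 | 29 − 21 = 8 | 7 | 5 |
| 4 days on/3 off | 28 | D25 | 29 − 25 = 4 | 3 | 4 |
| 5 days on/2 off | 28 | D26 | 29 − 26 = 3 | 2 | 5 |
| QD (reference) | 28 | D28 | 29 − 28 = 1 | 0 | continuous |

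On 2/2, 3/1, 2/1 and 7/7, which are still dosing on C2D6, the count is 6 if the biopsy follows that day's dose.

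**3. Illustrative drug remaining at a pre-dose C2D1 biopsy.** Fraction = 0.5^(gap × 24 h / half-life), relative to the level at the last dose. No human half-life is given. Section 1.1.1.1 gives 2.6 h (mouse) to 29 h (dog) after a single oral dose; 48 h and 96 h are assumptions that extend the range upward.

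| Gap | 2.6 h | 29 h | 48 h (assumed) | 96 h (assumed) |
|---|---|---|---|---|
| 1 day (QD) | 0.2% | 56% | 71% | 84% |
| 3 days (5/2) | <0.01% | 18% | 35% | 59% |
| 4 days (4/3) | <0.01% | 10% | 25% | 50% |
| 8 days (3/1, 2/1, 7/7) | <0.01% | 1% | 6% | 25% |
| 15 days (2/2) | <0.01% | 0.02% | 0.6% | 7% |

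These are drug fractions, not AR levels. They do not show what AR does.

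**4. Comparison with the re-timed PK visits.** PK day minus last dosed day of the preceding Cycle 2 on-block: 15 − 14 (2/2 and 2/1), 22 − 21 (3/1), 8 − 7 (7/7), 6 − 5 (5/2) and 5 − 4 (4/3). Each is 1 day, the same gap as a pre-dose C2D1 visit on QD. A visit with comparable time since last dose is therefore already in the schedule.

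**The case against.** A reader might infer that on intermittent schedules the biopsy measures AR recovery instead of degradation. The documents do not support that. It would need a human half-life and an AR resynthesis time, and neither is given. Section 1.1.1.1 reports a sub-nanomolar half-maximal degradation concentration, so a small residual amount of drug need not mean that AR has returned. It also reports that degradation is quick, and most of the permitted window lies after dosing has resumed, so many samples could be taken under renewed exposure. This objection stands. What remains is that timing relative to dose is not standardised, which holds whatever the half-life is.

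A reader might also infer that the choice of a Part B schedule would be biased against intermittent dosing. No between-schedule comparison of tumor AR is planned. The Safety Review Committee reviews safety, tolerability and available PK (Section 5.1.6), and biomarkers appear only among the emerging data that inform the expansion dose (Section 10.2). An effect on schedule choice is a possible risk, no more.

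The six schedules are not equally affected. On 4/3 and 5/2 only 3 and 2 drug-free days precede C2D1, and the window already reaches C2D5 and C2D6, just after the on-block.

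Finally, the biopsies are optional, the endpoint is exploratory, the starting frequency is QD, and intermittent dosing is used only if the committee approves it. All of this limits the weight of the point; none of it explains keeping C2D1.

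**Conclusion.** The point holds as a minor one. On the intermittent schedules a sample labelled on-treatment can be taken at any point from 3 to 15 days after the last dose up to 4 or 5 resumed doses (6 if post-dose on C2D6 where dosing continues). It does not reliably measure AR degradation during treatment, and results are not comparable between patients or schedules. The fault is chiefly on 2/2 (15-day gap) and on 3/1, 2/1 and 7/7 (8-day gap); it is slight on 4/3 and 5/2.

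The day counts rest only on the protocol's calendars, plus the assumption that the 5/2 and 4/3 patterns repeat in Cycle 2. The residual-drug figures rest on animal or assumed half-lives and a pre-dose biopsy, and are illustrative. No sample size, power or error rate is affected.

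**What to change.** Keep C2D1 (+5 days) for QD and BID. Amend Section 7.8.1 and footnote i of SOA 3, 4 and 5, with the matching table rows, so that on intermittent schedules the biopsy falls at the end of an on-drug block:
- 2/2 and 2/1: the last dosed day or the adjacent PK visit at C2D15.
- 3/1: the same, with C2D22.
- 7/7: the same, with C2D8.
- 4/3 and 5/2: narrow the present window to the end of the first Cycle 2 on-block. The adjacent PK visits (C2D5 and C2D6) are marked as if feasible in Tables 10 and 11, so they cannot be relied on for every patient.

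For all schedules, state whether the biopsy is pre- or post-dose and record the time since last dose, so that the analysis can account for it.

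The number of biopsies and the dosing are unchanged. The cost is later sampling on the longer schedules. At the PK visit the biopsy moves 7 days on 7/7, 14 days on 2/2 and 2/1, and 21 days on 3/1. In study days that is 28 + 8 = 36 on 7/7, 21 + 15 = 36 on 2/1, 28 + 15 = 43 on 2/2 and 28 + 22 = 50 on 3/1, against 29 on QD. Time on study at biopsy will then differ between schedules, and some patients may leave before an optional biopsy. Both should be reported with the results.
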